#### 5.6.2.4. Sensitivity Analyses of Key Secondary Endpoint Variables

In order to assess the robustness of more clinically relevant between-group comparisons for the analyses of the key secondary endpoints during the efficacy treatment period, the same statistical approach as described above in [Section 5.6.2](#) will be applied during the efficacy treatment period in the mITT population.

#### 5.6.2.5. Summary of Results by Time Point

Central laboratory values (in conventional (US) and international units), percent change from baseline, and/or when appropriate absolute change from baseline (in conventional and international units), for LDL-C, Total-C, HDL-C, fasting TG, and non-HDL-C at weeks 4, 8, and week 12 time points will be summarized by treatment group in both the ITT and mITT populations as described below. Central laboratory values (in conventional (US) and international units), percent change from baseline, and/or when appropriate absolute change from baseline (in conventional and international units), for Lp(a), Apo-B, Apo-A1 and ratio Apo-B/Apo-A1 (absolute change from baseline) at weeks 4, 8, and week 12 points will be summarized in the ITT and mITT populations as described below:

- For lipids other than TG and Lp(a): LS mean and SE for each treatment group, obtained from the same MMRM models as used for endpoints above and including planned time points (see [Section 5.6.2.1](#)) and with raw values, changes from baseline, and percent change from baseline as response variable in the model as appropriate.
- For lipids other than TG and Lp(a): Observed data raw values, change from baseline (as applicable), and percent change from baseline response variables will be summarized by patient counts, mean and SD for each treatment group at all planned time points.
- For TG and Lp(a): mean and SE for each treatment group obtained from multiple imputation approach followed by the robust regression models as used for endpoints above and including planned time points (see [Section 5.6.2.2](#)) and with raw values or percent changes from baseline as response variable in the model as appropriate.
- For TG and Lp(a): Observed data raw values and percent change from baseline response variables will be summarized by patient counts, mean and SD for each treatment group at all planned time points.

For the open-label period, central laboratory values (in conventional (US) and international units), percent change from baseline, and/or when appropriate absolute change from baseline (in conventional and international units), LDL-C, Total-C, HDL-C, fasting TG, and non-HDL-C, Lp(a), Apo-B, Apo-A1 and ratio Apo-B/Apo-A1 (absolute change from baseline) at weeks 18,

and 24 time points will be summarized by patient counts, mean and SD by all patients and by treatment group of the double-blind period (i.e., alirocumab, placebo) on the open-label population.

For patients receiving alirocumab in the double-blind period, central laboratory values (in conventional (US) and international units) including both the double-blind and open-label period assessments, percent change from baseline, and/or when appropriate absolute change from baseline (in conventional and international units), LDL-C, Total-C, HDL-C, fasting TG, and non-HDL-C, Lp(a), Apo-B, Apo-A1 and ratio Apo-B/Apo-A1 (absolute change from baseline) at weeks 4, 8, 12, 18, and 24 time points will be summarized by patient counts, mean and SD by all patients.

### **5.6.3. Adjustment for Multiple Comparisons**

In order to handle multiple key secondary endpoints during the double-blind period for the comparison of the alirocumab group and the placebo group, the overall type-I error will be controlled by the use of a hierarchical inferential approach. Statistical significance of the double-blind primary parameter at the 0.05 alpha level is required before drawing inferential conclusions about first key secondary parameter. Inferential conclusions about successive key secondary parameters require statistical significance of the prior one. The hierarchy testing sequence is the order of endpoints as presented in [Sections 4.6.1](#) and [4.6.2](#).

This fixed hierarchical approach will ensure a strong control of the overall type-I error rate at the 0.05 level during the double-blind period.

No further adjustments will be made for other secondary endpoints for which p-values will be provided for descriptive purpose only.

No adjustment will be made for the first-step and second-step statistical analyses ([Section 7](#)), since the primary and key secondary endpoints will have been concluded at the time of the first-step analysis.

## **5.7. Analysis of Safety Data**

The summary of safety results will be presented separately for the double-blind and open-label period. The double-blind period will be presented by treatment groups (alirocumab, placebo) on the safety population ([Section 3.2](#)). The open-label period will be presented by all patients and by treatment group of the double-blind period (i.e., alirocumab, placebo) on the open-label population ([Section 3.3](#)). No formal inferential testing will be performed for either period. Summaries will be descriptive in nature. All summaries of safety results described below will be presented for each period respectively, unless otherwise noted.

### ***General common rules***

All safety analyses will be performed, unless otherwise specified, using the following common rules:

- Safety data in patients who do not belong to the safety population (i.e., exposed but not randomized) will be listed separately.
- For the analyses of both double-blind and open-label periods, the baseline value is defined as the last available value obtained up to the date and time of the first double-blind study treatment, except otherwise specified.
- PCSA values are defined as abnormal values considered medically important by the Sponsor according to predefined criteria/thresholds based on literature review and defined by the Sponsor for clinical laboratory tests and vital signs (PCSA version dated January 2009 [\[Appendix 10.3\]](#)). Considering that the threshold defined in the PCSA list for monocytes and basophils can be below the ULN, the following PCSA criterion will be used for the PCSA analysis of monocytes and basophils:
  - PCSA criterion for monocytes:  $>0.7$  Giga/L or  $>\text{ULN}$  (if  $\text{ULN} \geq 0.7$  Giga/L).
  - PCSA criterion for basophils:  $>0.1$  Giga/L or  $>\text{ULN}$  (if  $\text{ULN} \geq 0.1$  Giga/L).
- PCSA criteria will determine which patients had at least 1 PCSA during the TEAE period, taking into account all evaluations including nonscheduled or repeated evaluations.
- The treatment-emergent PCSA denominator by treatment group for a given parameter will be based on the number of patients assessed for that given parameter at least once during the TEAE period.
- All measurements, scheduled or unscheduled, fasting or not fasting, will be assigned to analysis windows defined in [Appendix 10.2](#), [Table 1](#) and [Table 2](#) in order to provide an assessment for week 4 to week 24 time points.
- For quantitative safety parameters including central laboratory measurements and vital sign scores, descriptive statistics will be used to summarize results and change from baseline values by visit, the last on-treatment value and the worst on-treatment value. The last on-treatment value is defined as the last post-baseline value collected during the respective treatment period (as defined in [Section 4.7.1](#)). The worst on-treatment value is defined post-baseline as the nadir and/or the peak value collected during the respective treatment period, according to the direction (minimum or maximum) of the abnormality as defined in the PCSA list.
- Analyses performed according to diabetes status will be done considering diabetic patients as patients with either type 1 or type 2 diabetes in the medical history e-CRF page (regardless of the ongoing status).

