**Open-label Treatment:**

To provide further safety data in this rare patient population, all patients will participate in an open-label treatment period. Regardless of treatment assignment in the double-blind treatment period, patients will receive open-label study drug (alirocumab 150 mg SC Q2W) starting at week 12 (day 85) and continuing through week 24 (end of open-label treatment period, last injection of study drug on day 155/week 22). Patients who are receiving LMT or who are undergoing LDL apheresis should continue a stable dose and regimen and a stable LDL apheresis schedule and settings (as applicable) throughout the duration of the open-label treatment period.

Upon completion of the open-label treatment period, the sponsor may offer each patient the opportunity to participate in an additional lipid-lowering clinical trial. The patient and investigator may decline participation in further treatment trials.

Patients who do not participate in another lipid-lowering study will undergo an 8-week follow-up period. A follow-up phone call will be made at week 32 (corresponding to the 70 day follow-up) to collect AE and concomitant medication information.

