### 6. SELECTION, WITHDRAWAL, AND REPLACEMENT OF PATIENTS

#### 6.1. Number of Patients Planned

Approximately 74 patients with a 2:1 randomization to alirocumab and placebo are planned.

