#### 10.4.4.2. Laboratory Data and Vital Signs

The following definitions will be applied to laboratory parameters and vital signs:

- The baseline value is defined as the last available value before first dose of double-blind investigational study drug.
- The PCSA values are defined as abnormal values considered medically important by the sponsor according to predefined criteria/thresholds based on literature review and defined by the sponsor for clinical laboratory tests and vital signs.
- PCSA criteria will determine which patients had at least 1 PCSA during the TEAE period, taking into account all evaluations performed during the TEAE period, including unscheduled or repeated evaluations. The number of all such patients will be the numerator for the PCSA percentage.
- Double-blind treatment period: the treatment period used for quantitative analysis (laboratory results and vital signs) in the double-blind period is defined as the time from the first double-blind dose of the investigational study drug to the last double-blind dose of the investigational study drug + 21 days, or up to the first open-label dose of the investigational study drug, whichever comes first.
- Open-label treatment period: the treatment period used for quantitative analysis (laboratory results and vital signs) in the open-label study period is defined as the time from the first open-label dose of the investigational study drug to the last open-label dose of the investigational study drug + 21 days.

Summary statistics (including mean, median, Q1, Q3, standard error, minimum and maximum) of all laboratory variables and all vital sign parameters (raw data and changes from baseline) will be calculated for each visit, last and worst value assessed during the treatment period, and presented by treatment group. For selected parameters, mean changes from baseline with the corresponding standard error will be plotted over time (at same time points) in each treatment group.

The incidence of PCSAs at any time during the TEAE period will be summarized by treatment group for the double-blind study period, and by all patients and by the as-treated treatment group for the open-label study period, whatever the baseline level and/or according to the following baseline categories:

- Normal/missing
- Abnormal according to PCSA criterion or criteria

For laboratory parameters for which PCSA criterion is not defined, similar table(s) using the normal range could be provided.

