#### *Adverse Event Observation Period*

- Pre-treatment AEs are AEs that developed or worsened or became serious during the pre-treatment period.

- Double-Blind and open-label treatment-emergent adverse events are AEs that developed or worsened or became serious during the respective TEAE period.
- Double-Blind and open-label post-treatment AEs are AEs that developed or worsened or became serious during the post-treatment period.

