**Table 1: Definition of the patient status regarding hepatitis C virus**

Hepatitis C Antibody test result					
	Negative		Positive		
Reflexive test a – hepatitis C RNA test	Not available or HCV RNA not detected	HCV RNA detected	HCV RNA not detected b	HCV RNA detected	Not available
Hepatitis C status – label	Negative	Positive RNA	Negative b	Positive RNA	Positive Ab – no RNA available

a test performed at the same time or after the antibody test in pre-treatment period (for baseline evaluation), or post-baseline, respectively

b For post-baseline evaluation, a second antibody test with a different type of assay is to be done at the same date or after the first antibody test. The result of this test will modify the final hepatitis C status of the patient in some cases (see details in the text below the table)

The baseline evaluation will be based on tests performed during the pre-treatment period.

In case of multiple hepatitis C tests available for the post-baseline evaluation, the positive status of the patient will be defined as follows:

- “Positive RNA” status if at least 1 post-baseline positive RNA is detected, regardless of status of the patient at the end of treatment.
- Else “Positive Ab – no RNA available” status if no post-baseline reflexive RNA test is available for at least 1 post-baseline positive antibody test.

If no antibody test is available or with “indeterminate” as result pre-treatment or post-baseline respectively, the RNA test (if available) will be used alone to determine the status of the patient. If no RNA test is available then the hepatitis C status of the patient will be missing.

The post-baseline status “confirmed positive antibody with negative RNA” will replace “Negative” status as defined above in the case where no RNA was detected post-baseline and the 2 antibody tests surrounding the same visit (from 2 different types of assay) are positive.

For a conservative approach, the post-baseline status “Positive Ab – no RNA available” will not be modified by the availability of a second antibody test from a different assay.

For the description of the positive hepatitis C virus test during the TEAE period, all above rules will apply while replacing post-baseline by TEAE period.

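### For former-placebo patients the open-label safety baseline predates placebo, so baseline-referenced results mix change on placebo with change on alirocumab

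*SAP*

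**What the plan says.** **Design.** Protocol 6.1: "Approximately 74 patients with a 2:1 randomization to alirocumab and placebo are planned". Protocol 5.1 gives the purpose of the second period: "To provide further safety data in this rare patient population, all patients will participate in an open-label treatment period". It adds: "Regardless of treatment assignment in the double-blind treatment period, patients will receive open-label study drug", starting at Week 12.

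**Baseline.** SAP 5.7 (General common rules) states, for both periods, that "the baseline value is defined as the last available value obtained up to the date and time of the first double-blind study treatment". It leaves room for exceptions, but neither document sets a separate open-label safety baseline. SAP 4.7 and 6.1 agree with it. So does Protocol 10.4.4.2: "The baseline value is defined as the last available value before first dose of double-blind investigational study drug". For hepatitis C, SAP 5.7.2 says: "The baseline evaluation will be based on tests performed during the pre-treatment period".

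**How the baseline is used.** Under SAP 5.7.2 a patient has a laboratory PCSA (potentially clinically significant abnormality) if any value in the treatment-emergent period qualifies, and the main table splits patients by PCSA status at baseline. SAP 5.7.4 splits abnormal ECGs in the same way. Several criteria in SAP 5.7.2 and Appendix 10.3 are themselves changes from baseline. Open-label laboratory and vital-sign tables follow the double-blind layout and are shown for all patients and by former arm.

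**Adverse events.** These depend on timing, not on a baseline value: "Double-Blind and open-label treatment-emergent adverse events are AEs that developed or worsened or became serious during the respective TEAE period".

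**The concern.** For patients randomized to alirocumab, Day 1 is the last moment before the drug, and it is a sound reference throughout. For patients randomized to placebo, the last moment before the drug is Week 12. Measured from Day 1, their Week 24 result covers about 12 weeks on placebo and 12 on alirocumab, yet it sits in a table that describes the alirocumab period.

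What is at stake is attribution in a small safety database. The open-label period exists to add safety data. Under SAP 7, open-label safety data up to the cut-off already enter the first-step analysis intended for the submission dossier. In a rare-disease trial of about 74 patients, one or two patients in a cell can shape how a laboratory finding is read.

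**Working it through.** No figure in the plan depends on this rule, so there is none to reproduce. The check traces the rule through the tables, then sizes it under stated assumptions.

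**1. Patients concerned.** With 74 patients at 2:1 (Protocol 6.1), the placebo group is 74/3 = 24.7, about 25. Using all 25 assumes that every placebo patient enters the open-label period.

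**2. Is a pre-alirocumab value available?** Yes. Protocol Table 1 schedules haematology, chemistry, CPK, ECG, body weight, vital signs and hepatitis C antibody at Week 12. Footnote 6 in Protocol 8.1.1 places assessments first, then blood sampling, then dosing. During open-label treatment these are scheduled again only at Week 24, except vital signs, which are also taken at Week 18. (SAP 4.7.2 lists the hepatitis C antibody only at Weeks -2 and 12; Protocol Table 1 adds Week 24.)

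**3. What the baseline does to each result.**

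| Result | Role of baseline | Effect of the Day 1 reference in former-placebo patients |
|---|---|---|
| Laboratory PCSA, absolute threshold | Sets the baseline category only | Still counted under either baseline; a placebo-onset case sits under normal instead of abnormal |
| Haemoglobin, creatinine, weight, heart rate, blood pressure | Change from baseline is all or part of a criterion | The count itself can change, up or down |
| ECG | Sets the baseline category | As for absolute thresholds |
| ALT special-interest rule (SAP 4.7.1.2) | Selects 3 x ULN or 2 x baseline; enters the second directly, only if baseline ALT is at or above ULN | The applicable rule, or its cut-off, can change |
| Hepatitis C seroconversion | Requires negative baseline status | Misplaced only if RNA-positive, or RNA-negative with a positive second assay; an antibody result alone is not enough |
| Reported adverse events | None | No effect |

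**4. Haemoglobin examples (illustrative values), criterion a fall of at least 15 g/L.**
- False attribution: 150 g/L on Day 1, 133 at Week 12 on placebo, 133 at Week 24. Against Day 1: 133 - 150 = -17, counted. Against Week 12: 133 - 133 = 0, not counted.
- Masking: a rise of 10 on placebo, then a fall of 20 on alirocumab. Against Day 1: +10 - 20 = -10, not counted. Against Week 12: -20, counted.

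**5. Size of the false-attribution part.** Expected patients per parameter = n x p x q, where n = 25, p is the share who become abnormal on placebo, and q is the share of those still abnormal, with no further qualifying change, at an open-label assessment. The documents give neither p nor q; both are assumptions.

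| p | q = 0.5 | q = 1 |
|---|---|---|
| 2% | 25 x 0.02 x 0.5 = 0.25 | 0.5 |
| 5% | 0.625 | 1.25 |
| 10% | 1.25 | 2.5 |

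Against a pre-dose Week 12 baseline this excess is 0. For absolute thresholds and ECG, the figures are moves between baseline categories, not additions to the total.

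**6. A boundary problem.** SAP 4.7.1 ends the double-blind treatment-emergent period on the day before the first open-label dose. When dosing takes place at the Week 12 visit, the pre-dose sample is drawn on the next day by that count. By date alone, a value obtained on placebo could fall into the open-label period. SAP Appendix 10.2, Table 1a, does let the Week 12 window reach the day of the first open-label injection, but that governs by-visit summaries, not treatment-emergent PCSA counts.

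**The case against.** The strongest defence is that this is a deliberate and uniform convention. The SAP names its scope openly: "For the analyses of both double-blind and open-label periods, the baseline value is defined as the last available value obtained up to" the first double-blind dose. The protocol uses the same reference for laboratory data and vital signs, and SAP 5.6 uses it for efficacy. Change from study entry is a legitimate common scale. A second baseline would give the two open-label subgroups different reference days. The results are descriptive, former-placebo patients have their own column, and laboratory and vital-sign PCSA measurements are listed by patient, so a careful reader could trace an abnormality back to the placebo period.

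Much of this stands: the documents do not contradict themselves here, and no formal inference is at risk. Even so, the split by former arm isolates these patients without correcting their reference. The column for all patients mixes two kinds of baseline. The appendix PCSA table that ignores baseline status does not separate placebo onset from alirocumab onset. Neither document gives a reason for applying a pre-placebo reference to patients who first receive the drug at Week 12.

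It is also tempting to call the adverse-event rule and the laboratory rule contradictory. They are not: one classifies events by when they develop or worsen, the other counts any qualifying value in a period. The contrast shows only that laboratory and ECG findings lack the onset condition that protects the adverse-event tables.

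**Conclusion.** The point holds for baseline-referenced safety results of former-placebo patients in the descriptive open-label tables. It is a modest attribution problem with an inexpensive remedy. Under the assumed rates it amounts to about 0.25 to 2.5 patients per parameter among 25. The masking effect adds an amount that the documents do not allow one to estimate.

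A reader might infer more than the documents support:
- That every persistent abnormality becomes an extra count. Absolute-threshold PCSAs are counted under either baseline; only their category moves. Abnormalities that resolve before an open-label assessment are not counted at all.
- That placebo weeks are reported as alirocumab exposure. SAP 4.5 starts open-label exposure at the first open-label injection and combines periods only for patients given alirocumab in the double-blind period.
- That the bias runs only towards false signals. It can also hide a change on alirocumab.
- That a 24-week span inflates change criteria such as weight by a calculable amount. That needs a drift model, and the documents supply none; with stationary variation the longer span adds nothing.

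Reported adverse events and the randomized double-blind comparisons, including the primary result, do not depend on this choice.

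**What to change.** In SAP 5.7, 5.7.2 and 6.1:

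- For patients on placebo in the double-blind period, present open-label baseline-referenced safety results against the last value before the first open-label injection, normally pre-dose Week 12. Apply this to PCSA baseline category, change from baseline, the ALT special-interest rule, ECG shift and hepatitis C status.
- Assign pre-dose Week 12 values to the double-blind period.
- Keep the Day 1 baseline for former-alirocumab patients.
- Keep the Day 1 version for former-placebo patients as a supplementary table.
- Footnote the column for all patients to say which reference each subgroup uses.
- List the change in SAP 1.2.3, since it departs from Protocol 10.4.4.2.

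The cost is SAP wording, one derived baseline and one supplementary set of tables, from values already scheduled. The downside is that the two open-label subgroups will have different reference days, so the pooled column needs care in reading.
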